11.4 Procedures for Assessing Effectiveness

Effectiveness will be determined comparing patient-completed NEADL scale scores at 52 week follow-up between the two intervention groups.

Nottingham Extended Activities of Daily Living (NEADL) Scale³⁵

This is a patient-completed outcome measure of activities of daily living from the previous 4 weeks which has evidence of validity in stroke patients. The NEADL is a record of actual activity rather than capability, scoring patients in the areas of mobility, kitchen, domestic and leisure activities. A higher score indicates a greater level of independence. When assessed at baseline, it will assess the participant's functional capacity prior to hip fracture. When NEADL is administered the patient will be asked to recall the 4 weeks prior to hip fracture and not 4 weeks prior to completing this questionnaire. It will also be used at the 17 and 52-week follow-up assessment to assess the degree of functional recovery. The score range is 0 to 66 with higher scores indicating greater independence.

11.5 Secondary Objectives of Cost-Effectiveness and Mechanisms/Processes

Patient completed measures - secondary outcome

Hospital Anxiety and Depression Scale (HADS)³⁶

This is a patient-completed outcome measure of anxiety and depression. It is designed to measure anxiety and depression in patients with physical health problems. It has seven items related to common symptoms of anxiety and seven for depression. Patients are asked whether they experience the symptom definitely, sometimes, not much or not at all. The HADS was designed for use in the hospital setting but has been used successfully with the general population. This measure will be used at baseline and at the 17 and 52 week follow-up assessment. The two sub-scales have a range of 0 to 21 with higher scores indicating increased anxiety or depression.

Process measures

Abbreviated Mental Test Score (AMTS)³³.

The AMTS is a test with evidence of validity that is widely used in clinical and research settings in the UK for detecting and monitoring cognitive impairment. This will be used as a baseline description of the level of cognition. It is brief (ten items) and recommended for cognitive screening in acute settings in the Alzheimer's Society (2013) tool-kit³⁴ 'Helping you to assess cognition: a practical toolkit for clinicians'. It is generally considered to be easily administered and well tolerated by raters and subjects. This measure will be used at baseline and at the 17 and 52 week follow-up assessments. The score range is 0 to 10 with higher scores indicating worse cognitive function.

Visual Analogue Scale (VAS) for hip pain intensity³⁷

This is a patient-completed VAS of current hip pain intensity. Hip pain following surgery is an important factor affecting rehabilitation and will be measured at baseline and at the 17 and 52 week follow-up assessment. We have chosen a VAS as there is evidence of validity compared with the Oxford Hip Score whilst being simpler and quicker to complete, thus reducing the burden on patients. The range is 0 to 10 on a segmented line.

Falls Efficacy Scale - International (FES-I) (self efficacy)^{38,39}

The FES-I measures how concerned a patient is about falling when performing activities of daily living both inside and outside of the home. The scale details 16 activities which the patient must rate from 1 (not at all concerned) to 4 (very concerned) with regards to how concerned they would be about falling if they performed the activity. The range is 16 to 64 with higher scores indicating a greater fear of falling. The FES-I has been used successfully in older patients both without and with mild cognitive impairment and will be used to measure fear of falling in our trial at baseline, 17 and 52 week follow-up.

Visual Analogue Score - Fear of Falling (VASFoF)⁴⁰

This is a patient-completed VAS for fear of falling. A VAS is useful as it is easy to administer and brief. The range is 0 to 10 on a segmented line with higher scores indicating greater fear of falling. It has previously been used in older adults with and without cognitive impairment with good results and will be used to measure fear of falling in our trial at baseline, 17 and 52 week follow-up.

Grip strength⁴⁶

This is an objective measure of physical function that will be administered in a standardised manner by the researcher administering the patient-completed questionnaires. Grip strength correlates well with general fitness and muscle strength relating to physical function^{47,48}. It is also a more appropriate measure for use at baseline, as performing other physical assessments may carry risk to patients at this time point or would be likely to primarily reflect post-operative pain and not overall function. Grip strength will be measured at baseline and at the 17 and 52 week follow-up assessments.

Short Physical Performance Battery (SPPB)^{49,50}

This is a short series of physical function tests which assess lower limb function in terms of balance, gait, strength and endurance. The tests involve: examining the ability to stand with feet together in the side-by-side, semi-tandem and tandem positions; measuring the time to walk 8 feet (2.5m) and the time to rise from a chair and return to the seated position five times. Each test and a summary performance scale obtained by summing the categorical ranking on each test (0-12) were strongly associated with self-reported disability and were independent predictors of short-term mortality and nursing home admission. This was found even at the high end of the functional spectrum in those reporting almost no disability. This battery of tests was designed for use in people's homes and will be administered by the researcher at the 17 and 52 week follow-up assessments.

Health economic measures

EuroQol EQ-5D-3L (three levels)⁴¹

This is a patient-completed index of health-related quality of life, which gives a weight to different health states. It consists of five dimensions: mobility, self-care, usual activities, pain/discomfort, and anxiety/depression. Each has three possible responses. The responses record three levels of severity (no problems, /moderate problems, or severe problems) which is then converted to a health utility weight using UK norms. It also has a VAS ranging from 0 to 100 where the participant draws a line on the scale to rate their health state today. It will be used at baseline and at the 17 and 52 week follow-up assessments, and allows the calculation of quality-adjusted life years (QALY) using the area under the curve method which will be used as part of the economic analysis⁴².

Client service receipt inventory (CSRI)⁴³

The CSRI is a questionnaire for collecting retrospective information about trial participants' use of health and social care services, including voluntary services (e.g. charity services) and the components of the rehabilitation programme. This information will be combined with national sources of reference unit costs^{44,45} in order to calculate health and social care service costs for the economic evaluation. It will be used at baseline and at the 17 and 52 week follow-up assessments as part of the economic analysis. A reduced version of the CSRI will be used at baseline to reduce participant burden as participants are recovering from hip fracture surgery.

Carer completed measure - secondary outcome

Caregiver Strain Index (CSI)51

Carers who have been recruited into the trial will be asked to complete this measure. It is a 13-item tool that measures strain related to care provision. There is at least one item for each of the following major domains: employment, financial, physical, social and time. Positive responses to seven or more items indicate a greater level of strain. It can be used to assess individuals of any age who have assumed the role of caregiver for an adult aged 60 or over. It will be completed at baseline and at the 17 and 52 week follow-up. The range is 0 to 13 with a higher score indicating greater strain.

Hospital Anxiety and Depression Scale (HADS)³⁶

Carers will be asked to complete the HADS as a measure of their anxiety and depression at baseline and at the 17 and 52 week follow-up.

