3.3.2 Secondary Objective(s)

- 1. To compare the cost-effectiveness of an enhanced rehabilitation programme following surgical repair of proximal femoral fracture in older people compared with usual care, in terms of a cost-utility analysis from a health service and personal social care perspective.
- 2. To determine the effectiveness of an enhanced rehabilitation programme following surgical repair of proximal femoral fracture in older people compared with usual care, in terms of the performance of activities of daily living at 17 weeks follow-up.

- 3. To determine the effectiveness of an enhanced rehabilitation package following surgical repair of proximal femoral fracture in older people compared with usual care, in terms of anxiety and depression at 17 and 52 weeks follow-up.
- 4. To assess whether the enhanced rehabilitation intervention creates change in self-efficacy, hip pain, cognitive function, fear of falling and physical function as potential mediators for improving activities of daily living.
- 5. To assess whether the enhanced rehabilitation intervention creates change in care-giver strain, anxiety and depression in carers.
- 6. To determine the mechanisms and processes that explains the implementation and impacts of the enhanced rehabilitation programme.

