3.4 Outcome measures/endpoints

Each measure to be used for the outcomes described in this protocol has been chosen due to their recognised use with patients in measuring physical and mental health status. Each measure is either validated or researched for use.

Routinely collected data will be used to collect information about demographics. Participants' cognitive function will be assessed using the Abbreviated Mental Test Score (AMTS)³³. At baseline, 17 and 52 weeks outcome measures will be completed by participants with assistance from a member of the research team blinded to participant allocation. Objective measurement of physical function will be assessed by the researcher at baseline, 17 weeks and 52 weeks using the grip strength test. At 17 and 52 weeks follow up, a researcher will measure physical function using the Short Physical Performance Battery (SPPB) of tests in the patient's home. Qualitative interviews will take place with patient's carers after 17 weeks to gather feedback on trial participation and intervention design.

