3.4.2 Secondary Outcome/Endpoints

Secondary endpoints include:

Efficacy:

- 1. Anxiety and depression (HADS) ³⁶
- 2. Cognitive status (AMTS)³³
- 3. Hip pain intensity at (VAS) for hip pain intensity³⁷
- Falls self-efficacy (FES-I) (self-efficacy)^{38,39}
 Fear of falling (VASFoF)⁴⁰
- 6. Physical function (SPPB)^{49,50}
- 7. Grip strength⁴⁶

Carer behaviours may make an important contribution to the intervention's effectiveness. We will also include items to measure care tasks and roles in terms of the type of support provided and the number of hours spent providing support. We will ask about help with the workbook, goal-setting and the practice of rehabilitation exercises as well as more general assistance.

Carer of patient:

- 8. Care-giver strain (CSI)⁵¹
- 9. Care-giver anxiety and depression(HADS)³⁶

Safety:

- 10. Number of adverse events across the two arms
- 11. Number of serious adverse events across the two arms
- 12. Number of re-admissions to hospital following hip-fracture repair surgery

Health Economics:

- 13. Incremental cost-utility ratios, EuroQol EQ-5D-3L (three levels)⁴¹
- 14. Health service and personal social care Cost-utility, (CSRI)⁴³

Process Evaluation:

- 15. Refine the programme theory that was generated from the previous realist review when developing the intervention programme
- 16. Investigate therapists' expectations and experience of implementation, identifying the actual practices, likely tailoring and interactions that took place within the trial setting. Also, investigate therapists' skill level, relevant training, previous experience and level of familiarity of working in this sector. Finally, investigate therapists learning over time and its potential impact on outcomes.
- 17. Investigate the mechanisms driving and shaping the tailoring of the enhanced rehabilitation programme to individual patients and its possible impacts on outcomes.
- 18. Investigate trial participants' experiences and views about their involvement in the FEMuR trial.
- 19. Synthesize all data collected and link it to the explanation of trial findings in relation to the refined programme theory.

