7.2 Informed Consent

Informed consent is a process initiated prior to an individual agreeing to participate in a trial and continues throughout the individual's participation. Informed consent is required for all individuals participating in CTRC coordinated trials. In obtaining and documenting informed consent, the investigator should comply with applicable regulatory requirements and should adhere to GCP and to the ethical principles that have their origin in the Declaration of Helsinki.

In Wales, Welsh versions of the Patient Information and Consent Forms (PISC) will be available. Patient and carer participants will be given ample time to decide whether to join the trial or not but should be randomised within 4 weeks of hip fracture repair surgery. Participants who are not able to decide in this time will not be able to take part. Participants will be asked to sign one of the following consent forms:

- FEMuR III patient participant informed consent form (English)
- FEMuR III patient participant informed consent form (Welsh)
- FEMuR III carer participant informed consent form (English)

• FEMuR III carer participant informed consent form (Welsh)

Potential participants will be introduced to the trial and given a participant information sheet and consent form (PISC). Potential participants with mild dementia and cognitive impairment will be included, so long as they maintain the mental capacity to give informed consent. It will not depend upon the Abbreviated Mental Test Score, which is being used as an outcome measure for cognitive functioning. The capacity of patients to give informed consent will be decided by clinical staff on the orthopaedic wards. If however, potential participants score low on this score (8 or less) during follow-up, the researchers should then inform the PI and a clinician will be asked to reassess mental capacity and no further trial information can be collected until a PI or delegated other can confirm patient has capacity. Some potential participants will lack capacity because of a post-surgery temporary delirium. These people will be monitored closely and may need repeat visits from the research network staff until the temporary delirium has settled in order to obtain informed consent. These repeat visits may need to follow the potential participant after they have been discharged from the acute orthopaedic ward onto another ward, or another hospital, or after they have been discharged home.

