- Can the person use or weigh that information as part of the process of making the decision (which can be assessed by inquiring of the person's understanding or potential options for participation)?
- Is the patient able to communicate his/her decision?

If the question is no to one or more of these questions, the patient will not be approached as they do not meet the eligibility criteria for inclusion in the trial. Also although the AMTS will not be used to determine eligibility, if the person has a low score then the clinician will be asked to re-assess capacity.

Some of the potential participants will initially be ineligible because of a temporary delirium. These people can be re-assessed several days later when the delirium has settled. The research team can maintain contact even if the patient is transferred to another ward for in-patient rehabilitation, or discharged home.

The mental capacity of participants may change. If the participant no longer has capacity when arranging a follow-up visit, no further data can be collected until the participant has been assessed as regaining capacity. Baseline data and other data collected up to that point will be used in the analysis.

Many of the participants can be classified as vulnerable adults. The clinicians and researchers in contact with them will have received statutory protection of vulnerable adults (POVA) training. This will be reported on a trial training log. A mechanism of immediate risk assessment and onward referral to appropriate authorities and police has been developed within the framework of the Human Rights Act 1998 and Data Protection Act 2018 if abuse or neglect is suspected, observed or disclosed by the participants.

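### Section 11.5 gives the direction of the Abbreviated Mental Test Score as higher = worse, which contradicts sections 7.2 and 12.2, where a low score is the sign of concern

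*Protocol*

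**What the plan says.** Section 11.5 describes each scale in turn. For the AMTS, a ten-item test given at baseline, 17 and 52 weeks, it says: "The score range is 0 to 10 with higher scores indicating worse cognitive function".

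Two other sections use the same score. Section 7.2 sets out what follows when "potential participants score low on this score (8 or less) during follow-up": the researchers tell the PI, a clinician re-assesses capacity, and "no further trial information can be collected until a PI or delegated other can confirm patient has capacity". Section 12.2 says that the AMTS does not decide eligibility, but that "if the person has a low score then the clinician will be asked to re-assess capacity".

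The score also has a place in the analysis. Section 3.4.2 lists "Cognitive status (AMTS") as the second secondary efficacy endpoint. Section 3.4 names the AMTS as the measure of cognitive function. Secondary objective 4 in section 3.3.2 asks whether the intervention "creates change in self-efficacy, hip pain, cognitive function, fear of falling and physical function as potential mediators" for activities of daily living. Section 11.3 assigns continuous secondary outcomes at 17 and 52 weeks to ANCOVA adjusted for baseline score, allocation group and stratification variables.

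**The concern.** The section that defines the outcome scales and the two sections that act on the score imply opposite directions. Section 11.5 is the only explicit statement of direction for the AMTS, so it is the natural source for whoever writes the SAP, the Coding Specification or the results tables.

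Nothing around the sentence would alert that person. The HADS, FES-I, fear-of-falling VAS and Caregiver Strain Index are all described in the same section as higher = worse, so the AMTS sentence looks like one more of the same kind.

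What is at stake is the interpretation of one named secondary endpoint. If the instrument is scored so that low is poor, as 7.2 and 12.2 assume, and the result is read by 11.5, then a difference favouring the intervention would be described as favouring usual care, or the reverse.

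**Working it through.** There is no figure in the plan to reproduce. The check is one of logic, from the protocol alone.

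**1. Direction, section by section**

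| Section | What it states or implies | Poor cognition lies at |
|---|---|---|
| 11.5 | Stated: higher is worse | High end |
| 7.2 | Implied: 8 or less is low and prompts re-assessment of capacity | Low end |
| 12.2 | Implied: a low score prompts re-assessment of capacity | Low end |

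**2. Which values the trigger in 7.2 covers**

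A score from 0 to 10 has 11 possible values. The condition of 8 or less covers 0, 1, ..., 8, which is 9 values, and leaves out 9 and 10, which is 2 values (9 + 2 = 11).

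- If higher were worse, as 11.5 says, the trigger would cover the 9 best values and leave out the 2 worst. A prompt to re-assess capacity would then have no sensible purpose.
- If lower is worse, the trigger covers every value except the 2 best. That agrees with its stated purpose.

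So 7.2 and 12.2 agree with each other, and 11.5 is the odd one out.

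**3. What a wrong label does to the ANCOVA**

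Write the model as Y = α + τT + βX + (stratification terms) + error, where Y is the follow-up AMTS, X the baseline AMTS and T the allocation. The label higher = worse appears nowhere in this model. The estimate of τ, its standard error, confidence interval and p-value are the same whichever label is attached. Only the words change: whether τ > 0 is called benefit or harm.

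For comparison, suppose the score were actually recoded as Y' = 10 − Y and X' = 10 − X. Substituting gives Y' = constant − τT + βX' + ..., so the estimate becomes −τ with the same standard error and p-value, and the interval is mirrored about zero. The protocol does not ask for this recoding.

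**4. What it does to a mediated effect**

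Let a be the effect of allocation on AMTS, and b the effect of AMTS on NEADL given allocation. The indirect effect in a linear model is a × b.

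- Relabelling without recoding leaves a, b and a × b as they are.
- Recoding gives a' = −a and b' = −b, so a' × b' = (−a)(−b) = a × b.

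The indirect effect keeps its sign and size in both cases. Only the verbal reading of each single path could be reversed.

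**5. What it does to the trigger**

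Section 7.2 gives the trigger as a number. A researcher who totals the ten items in the usual way and applies 8 or less flags the same participants whatever 11.5 says about direction. Other participants would be flagged only if someone reverse-scored the test, and no section tells them to.

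**The case against.** The strongest reply accepts the contradiction and disputes its weight. The AMTS is one of seven patient efficacy secondary endpoints. Section 11.5 places it among the process measures and speaks of it as a description of cognition at baseline. Section 13.2 leaves derivations and validations to a Coding Specification, and section 11.3 leaves the analysis detail to a SAP. Neither is at hand, and either may state the direction correctly. Staff familiar with the test may also notice the slip.

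Much of this stands. It limits the consequence to a possible misreading of one secondary measure, and it means that nobody can say the error will reach the results. It does not remove the error: the protocol states a direction, and states it against its own sections 7.2 and 12.2.

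A reader might infer three stronger things, and the protocol supports none of them.

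- **That the treatment effect on AMTS would be reversed in the analysis.** The fitted estimate does not depend on the label (step 3). Only the description of its sign does.
- **That the mediation result would change sign.** The indirect effect is unchanged (step 4). The protocol also fixes no mediation model; objective 4 asks only whether the potential mediators change.
- **That the wrong participants would be referred for re-assessment of capacity.** The trigger is numeric, and both sections that govern it call the score low (step 5). This would need reverse scoring that the protocol nowhere asks for.

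**Conclusion.** The sentence in 11.5 is wrong as written, because it cannot be reconciled with 7.2 and 12.2. It is an internal inconsistency in a scale description, not a choice of analysis, and its severity is minor to moderate.

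Its reach is the wording of the AMTS result at 17 and 52 weeks, where benefit and harm could be exchanged in a report that follows 11.5. No numerical bias can be attached to it: the estimate, its interval and its p-value are identical under either label. NEADL scoring, the sample size, eligibility and randomisation are untouched.

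The conclusion rests on one assumption, that a low score prompts re-assessment because it indicates poorer cognition. That is the only reading under which 7.2 and 12.2 make sense. It does not rest on any outside source about the test, and it implies nothing about whether the re-assessment rule or its cut-off is appropriate.

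**What to change.** In section 11.5, change the direction so that higher AMTS scores indicate better cognitive function, in agreement with 7.2 and 12.2. Then check that the Coding Specification, the data-entry guidance and the SAP carry the same direction, and that the shells for the AMTS tables say which sign favours the intervention.

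The cost is one word in the protocol, which can go in with the next amendment, and a short check of the related documents. No data collection, sample size or analysis model changes. The capacity rule in 7.2 and 12.2 is left as it stands; the only request is that the three sections agree on the direction of the scale.
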